7.2 SAMPLE SIZE CONSIDERATIONS

- Due to the short 1-month duration of participation, subject withdrawal from the study is not anticipated to be significant.
- The proposed sample size (40/condition) is consistent with those recommended for small intervention tests in staged intervention development.⁶⁵ Based on administrative data for 54,466 hospitalizations in 2014, 1,037 hospitalizations involved implementation of CIWA protocols (indicating moderate to severe alcohol use) and 719 involved a diagnosis of an opioid use disorder. We expect that the majority (at least 1400) of these are unique patients, suggesting that about 117 patients per month will be identified through EPIC, with more referred directly by physicians and social workers. Although, we believe our enrollment rate of 16 per month over 5 months is realistic, if not conservative, this pilot provides the opportunity to confirm feasibility of this enrollment rate.

- It is not feasible to blind the staff to study condition because the study condition requires specific care by the START. While it is likely (and expected) that medical teams will treat patients in both the experimental and usual care (UC) conditions, patients in the START will have an enhanced experience because they (unlike patients in the UC condition) will be receiving START components designed to increase their readiness to take the medication and link to follow-up care. Moreover, the support provided by the START to medical teams for each START patient is the component that we hypothesize will take the burden off of the medical team and increase the likelihood of the patient receiving medication. Even as medical teams become more aware of medication for OAUD and perhaps increase prescribing, we hypothesize that patients whose medical teams receive support for their START patients will still be more likely to receive medication, even if medical teams are aware they can prescribe these medications. Thus, over time, while we might see increased medication initiation for patients in both study conditions, we still hypothesize statistically and clinically significant differences for patients in the CCT group. Nevertheless, we still plan to safeguard against any biases and effects of UC patients receiving the START. The research team will review electronic health record data to determine whether the START AMS or CM accidentally treated UC patients. Further, as part of this developmental study and pilot test, we are carefully assessing whether (and why) contamination occurs and, if it does, we will take additional steps to further safeguard the experimental condition in the future RCT.

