4.0 STUDY DESIGN AND METHODS

- Eligibility screening - Assessments, demographics (conducted in person or remotely)
- Informed Consent, if eligible (to be obtained in person either on paper or electronically using an approved platform or remotely using an approved platform)
- Enrollment - the CSMC study staff will enroll consented, eligible patients.
- Baseline interview - after enrollment, the CSMC approved study staff will conduct an in-person or remote 30-40-minute baseline interview. Interview data will be recorded on a tablet or computer into a web-based survey system (REDCap). Patients will be compensated with a \$50 Forte payment card (given in person or mailed).
- Randomization - following consent and the baseline interview, the CSMC approved study staff will randomize the patient to the START or UC arm using REDCap.
- All patients will be given patient education materials on alcohol and/or opioid use disorder, as well as harm reduction materials (OUD only). If the visit is remote, the research team will give these materials to a member of the medical team to deliver to the patient or place them in the patient's room.
- 1-month post discharge follow-up interview - the CSMC approved study staff will conduct a follow-up interview by telephone 1-month after the patient is discharged from the hospital. Patients will receive \$50 loaded onto their existing Forte payment card for participation.

The components of the START workflow process are as follows (also shown in Figure 2):

[figure not shown]
1. Triage (Care Manager CM and Addiction Medicine Specialist AMS):
The CM assesses the patient for acute biomedical needs related to the OAUD. The AMS addresses acute biomedical needs (e.g. facilitates withdrawal management).
2. Engage, assess, plan (CM and AMS) (conducted in person or remotely based on circumstances):
3. If there is not an urgent need for medical intervention or after the urgent medical need is addressed, the CM and/or AMS:
 - engages with the patient (CM and AMS)
 - conducts a diagnostic and biopsychosocial assessment (CM)
 - conducts a complete biomedical assessment and addresses comorbidities (AMS)
 - delivers the brief negotiated interview (BNI), an evidence-based intervention, to assess to increase readiness and develops a plan for initiating evidence-based treatment for OAUD (MAT) and/or psychosocial treatment) during and after the hospital stay (CM)
 - ensures the patient understands the follow-up plan and addresses barriers (CM).

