 - (3) Whether a START is feasible and acceptable with in the inpatient medical setting. These knowledge gains will provide invaluable, preliminary information on how to improve the quality of care for hospitalized patients with OAUD and on how to address an unmet need that has severe individual and societal consequences. The knowledge obtained in the study (and even more so in the larger, subsequent RCT) not only will benefit individual patients who participate in the study but also hospitals looking for a pragmatic and feasible way to improve OAUD care. On a societal level, providing a new way to identify and initiate treatment for patients with OAUD could fill a previous unmet need and bring down healthcare costs related to untreated OAUD. We believe that the long-term gains of the study, in terms of knowledge and substantive gains to the community, far exceed any risks for participants.

Table 2: Flowchart of Procedures

Research Procedures	Baseline visit	During course of hospital stay	1-month post-discharge
Eligibility	R		
Informed Consent	R		
Randomization	R		
Sociodemographic Data	R		
Mental health symptoms (PHQ-9, GAD 7); pain (PEG); substance use (WHO ASSIST, NSDUH) consequences of use (SIP-AD), service utilization (NSDUH, GAIN), stigma (SASS)	R		R
Satisfaction with START intervention ^a			R
Medication for alcohol or opioid use disorder ^b		S	
Therapy for alcohol or opioid use disorder ^b		S	
START Addiction Medicine Specialist (AMS) coordinates team-based care ^c		R	R
START Care Manager (CM) ^c coordinates team-based care		R	R

LEGEND

R = Research item/procedure done only for research purposes and covered by the study

S = Standard of care item/procedure that is part of regular care and billed to the patient/insurance

Footnotes:

- a. Only for patients randomized to the START intervention arm of the study.
- b. For both groups: Usual Care and Start intervention. Includes Brief Negotiated Interview and addiction focused discharge planning and follow-up.
- c. The START intervention utilizes established standard-of-care services and procedures (care manager, addiction medicine specialist, medication treatment, therapy, etc.) and helps integrate them into the patient's care in a systematic way. It is this planned coordination and integration that are the intervention, not the services themselves.

- A list of written materials that will be part of the research is included in Appendices - section 8.0 below.

Behavioral Intervention

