5.3 VARIABLES COLLECTED

- The following data points/variables will be collected:

Baseline Measures:

Variable	Source Document
Demographics 
 • Age • Sex (Biological at Birth) • Gender (Identity) • Race/ethnicity • Housing status • Marital status • Income • Education 	Demographics Form
Mental Health Symptoms 
 • Depression • Anxiety 	PHQ-9 survey ^{51,52} GAD 7 survey ⁵³⁻⁵⁵
Pain intensity and frequency	PEG ⁵⁶
Alcohol/Opioid Diagnosis	WHO ASSIST ⁵⁷
30-day Alcohol/Opioid Use: National Survey on Drug Use and Health 30-day use questions	Patient Survey (Adapted from NSDUH ⁵⁸)
SUD Treatment Utilization	Patient Survey (Adapted from NSDUH ⁵⁸)
Healthcare Utilization Related to SUD	Patient survey (Adapted from GAIN ⁵⁹)
Employment	Patient Survey
Negative Consequences	Short Inventory of Problems Alcohol and Drugs (SIP-AD) ⁶⁰
Patient Experience of Stigma	Adapted from Grosso et al. 2019. ⁶¹ Questions to assess stigma experience.
Self- Stigma	Substance Abuse Stigma Scale (SASS) ⁶²
Receipt of START Intervention Components (Patient)	
START Intervention Received (Assessment, Engagement, Treatment/Discharge Planning); Length of Intervention (hours)	START Patient Registry
START Intervention Follow Up Received (Number of follow up calls made)	START Patient Registry

Follow-up Survey Measures (Patient)	
Mental Health Symptoms 
 Anxiety Depression 	PHQ-9 Survey ^{51,52} GAD 7 Survey ⁵³⁻⁵⁵
30-day Alcohol/Opioid Use: National Survey on Drug Use and Health 30-day use questions	Patient Survey (Adapted from NSDUH ⁵⁸)
SUD Treatment Utilization	Patient Survey (Adapted from NSDUH ⁵⁸)
Healthcare Utilization Related to SUD	Patient survey (Adapted from GAIN ⁵⁹)
Negative Consequences	Short Inventory of Problems Alcohol and Drugs (SIP-AD) ⁶⁰
Employment	Patient Survey
Patient Experience of Chronic Illness Care	PACIC ⁶³
Satisfaction with START intervention	Patient Survey
Provider Interviews (Provider)	
Acceptability/feasibility of START Intervention (Provider Interview Guide)	Provider Interview Guide

Outcome Measures:

Outcome	Measure, Assessment (Type of Variable)	Data Source
Primary Outcomes		
In-hospital MAT initiation	Received an OAUD MAT between admission and discharge (Binary)	CSMC admin data
Linkage to follow-up care	Received at least one visit post-discharge for MAT and/or psychosocial care for OAUD (Binary)	Appointment dates 1-month interview

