b. 1-month follow-up. 1-month follow-up interview data will be collected by telephone, encrypted on a password-protected tablet that is connected to the survey through REDCap, only identified by study ID. Data will be collected by the CSMC approved study staff and entered directly into the secure tablet. The CSMC project manager will transmit baseline data (identifiable only by study ID) to RAND via secure file transfer protocol (SFTP) site. A program, such as PGP, that provides RSA-level security will be used to encrypt files. These data will not be shared with individuals who are not part of the project team, and no data shared with any members of the project study team will contain participant names.

4. CSMC administrative data. CSMC administrative data will be pulled from the electronic medical record system, EPIC, via a request submitted to the Research Informatics and Scientific Computing Core (RISCC). The CSMC project manager will replace all medical record numbers with study IDs. The CSMC project manager will then transmit the administrative data to RAND via the SSH File Transfer Protocol (SFTP) which is a network protocol that provides file access, file transfer, and file management functionalities over secure connection. It was designed by the Internet Engineering Task Force (IETF) as an extension of the Secure Shell protocol (SSH)

version 2.0 to provide secure file transfer capability.

D. Disclosure Risks

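### The reason given for not blinding staff covers care delivery, not the 1-month telephone interviewer, whose knowledge of the arm could bias days of use and, in part, linkage

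*Combined protocol and SAP*

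**What the plan says.** Section 7.2 contains the protocol's only statement on blinding: "It is not feasible to blind the staff to study condition because the study condition requires specific care by the START". The text that follows is about medical teams treating patients in both arms and about contamination. The safeguard it offers is a review of health records for usual-care patients treated by START in error.

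Section 4.0 says that, after consent and the baseline interview, "the CSMC approved study staff will randomize the patient to the START or UC arm using REDCap". For the outcome call it says that "the CSMC approved study staff will conduct a follow-up interview by telephone 1-month after the patient is discharged from the hospital". The data-safeguarding text on the 1-month follow-up in Section 6.1 adds: "Data will be collected by the CSMC approved study staff and entered directly into the secure tablet".

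Table 2 in Section 4.0 places satisfaction with START at the 1-month time point, with the footnote "Only for patients randomized to the START intervention arm of the study". Section 5.3 lists the same item among the patient follow-up survey measures.

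The outcome table in Section 5.3 names three primary outcomes. In-hospital medication initiation comes from hospital administrative data. Linkage to follow-up care has the source entry "Appointment dates 1-month interview". Past-30-day heavy drinking or opioid use comes from the baseline and 1-month interviews.

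**The concern.** The stated obstacle to blinding is that START involves visible, specific care. Section 4.0 assigns that care to the care manager and the addiction medicine specialist. It gives the 1-month interviewer no care task, so the obstacle does not explain why the interviewer should know the arm. The plan gives no other reason and describes no masking.

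Patients will know their arm, so some reporting bias cannot be removed. The interviewer's contribution can be reduced. Someone who knows a patient had START may, without meaning to, follow up a vague answer about a visit or a count of days differently from one given by a usual-care patient. Days of use has no second source. Linkage has one, but its origin and precedence are not stated.

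At stake are the effect estimates for two of the three primary outcomes. Section 2.0 sets out to test improvement in linkage and clinical outcomes. The Innovation text in Section 4.0 wants to learn whether START reduces substance use. Section 7.2 expects differences of statistical and clinical importance, at least for medication initiation.

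**Working it through.** **Tracing the roles.** The plan has no figure of its own to reproduce here, so the main check sets the sections side by side.

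- *Who knows the allocation?* The approved study staff who randomize in REDCap (Section 4.0).
- *Who makes the 1-month call and enters the data?* The same role (Sections 4.0 and 6.1).
- *Is the caller separated or masked anywhere?* No such provision is stated. The nearest measure is training in standardized, objective data collection (Section 6.1, part IV), which does not hide the arm.
- *Does the follow-up reveal the arm?* Yes, at some point: the START-only satisfaction item cannot be directed to the right patients without knowing the arm.
- *Which primary outcomes pass through the call?* Days of use wholly, linkage partly, medication initiation not at all.
- *Does baseline adjustment (Section 7.1) remove the problem?* No. The baseline interview precedes randomization, so arm-related interviewer error can enter only at follow-up, where it goes into the treatment coefficient.

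**Illustrative size, days of use.** From the documents: 40 per arm (Section 7.2). Assumed: no missing data, no true effect, two-sided alpha 0.05, normal approximation, unadjusted comparison, and a differential reporting shift of 0.1 to 0.2 SD.

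SE of the mean difference = √(2/40) = 0.224 SD.

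P(reject) = Φ(−1.96 + b/SE) + Φ(−1.96 − b/SE)

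| Shift b | b/SE | P(reject), no true effect |
|---|---|---|
| 0.1 SD | 0.45 | 7.3% |
| 0.2 SD | 0.89 | 14.5% |

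If the SD were 10 days (also an assumption), these shifts would be 1 to 2 days in 30.

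**Illustrative size, linkage.** Assumed: the same true rate p in both arms, from 20% to 50%, and a fraction f of 5% to 15% of unlinked START patients recorded as linked. The recorded START rate is p + (1 − p)f.

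- p = 50%, f = 5%: 0.50 + 0.50 × 0.05 = 0.525. Odds ratio (0.525/0.475)/(0.50/0.50) = 1.11.
- p = 20%, f = 15%: 0.20 + 0.80 × 0.15 = 0.32. Odds ratio (0.32/0.68)/(0.20/0.80) = 1.88.

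The spurious differences are 2.5 and 12 points. The standard error of a difference at a common rate is √(2 × 0.25/40) = 11.2 points at 50% and √(2 × 0.16/40) = 8.9 points at 20%. These figures assume that appointment dates correct none of the misrecording, so they overstate the problem if that source is used well.

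**Effect on the variance goal.** A constant shift in one arm leaves the variance of a continuous outcome unchanged. For linkage the variance term p(1 − p) moves with the recorded rate: 0.250 to 0.249 in the first case above, 0.160 to 0.218 in the second.

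**The case against.** The strongest reply rests on the purpose of the pilot. Section 7.1 does not expect enough power to detect effects. It puts first the variability of the effect estimate, for use in planning a later trial, and the detection of areas of concern. A uniform reporting shift hardly touches that variability for days of use, and shifts of 0.1 to 0.2 SD are smaller than one standard error. This stands, and it limits the weight of the point. It does not remove it, because the aims in Sections 2.0, 4.0 and 7.2 concern the effects themselves.

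The blinding sentence may also be meant only for staff who deliver care. The plan would then be silent on interviewers, not mistaken about them. That is a fair reading, and the remedy is the same: say so, and say what applies to the interviewer.

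A reader might infer more than the documents support:

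- *The same individuals randomize and call.* The documents show a shared role, not shared people, and they never describe the interviewers as unblinded.
- *The allocation is visible to callers in REDCap, or the satisfaction item comes before the outcomes.* The REDCap build is not shown and the follow-up survey is a separate document (Section 8.2). Section 5.3 lists satisfaction last among the patient follow-up measures. That does not establish interview order, but a suitable order may already be in use.
- *Both outcomes are purely self-reported.* Linkage also draws on appointment dates.

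Staff training in objective collection is a real mitigation, though not a substitute for masking.

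**Conclusion.** The point holds in a limited form. The reason given for not blinding does not reach the 1-month interviewer, no masking of that person is described, and the follow-up contains an item that discloses the arm. Interviewer knowledge could bias the effect estimate for days of use and, to the extent that linkage relies on the interview, for linkage too. Medication initiation is not affected by this route.

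The size is unknown. Under the stated assumptions, a shift of 0.1 to 0.2 SD in days of use is about half to nine tenths of a standard error. It would raise a nominal 5% false-positive rate to between 7.3% and 14.5%. The linkage illustration spans spurious odds ratios of 1.11 to 1.88 and depends on the assumed rates and on no correction from appointment dates.

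It would be too strong to conclude that bias has been shown or that the pilot cannot serve its planning purpose. The documents establish neither, and the variance goal is much less exposed. This is a worthwhile, inexpensive improvement to conduct and reporting.

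**What to change.** 1. In Section 7.2, limit the statement on blinding to staff who deliver care, and state separately what applies to the 1-month interviewer.
2. Set REDCap user rights so that the interviewer cannot see the allocation field.
3. Open the START-only satisfaction items only after the use and linkage items have been saved. If the survey already works this way, say so in the protocol.
4. Where existing staffing allows, have the call made by someone who did not randomize that patient.
5. Record for each call whether the interviewer became unmasked, and when.
6. State where appointment dates come from and which source prevails, and check linkage against them in the same way in both arms. The care manager's calls to outpatient providers are part of START, so they cannot be the check unless an equivalent is done for usual care.

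The cost is a change to REDCap permissions and branching, a call rota and a few lines of text. The downsides are less flexible scheduling and incomplete masking, since patients know their arm and may disclose it. The documents do not give the number of study staff. If one person does all these tasks, keep the REDCap and item-order changes and report interviewer awareness as a limitation.

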8.0 APPENDICES (MAY BE FOUND AS SEPARATE DOCUMENTS AS LISTED BELOW)

8.1 RECRUITMENT AND ENROLLMENT

- ELIGIBILITY SCREENER
- ELIGIBILITY CHECKLIST
- STUDY PHYSICIAN FLYER
- PHYSICIAN SCREENING CARD
- PHYSICIAN RECRUITMENT LETTER
- PHYSICIAN TO PATIENT LETTER
- PATIENT & FAMILY EDUCATION MATERIALS

8.2 EVALUATION

- BASELINE SURVEY
- FOLLOW-UP SURVEY
- PROVIDER INTERVIEW INFORMATION SHEET
- PROVIDER INTERVIEW GUIDE

8.3 INTERVENTION

- START MANUAL & APPENDICES
 - APPENDIX A: START ROLES AND RESPONSIBILITIES TABLE
 - APPENDIX B: START ASSESSMENT FORM
 - APPENDIX C: REGISTRY INSTRUCTIONS
 - APPENDIX D: CARE MANAGER HANDOUTS
 - APPENDIX E: START REFERRAL RESOURCE GUIDE
 - APPENDIX F: MEDICATION ASSISTED TREATMENT START CARDS – ALCOHOL USE DISORDER
 - APPENDIX G: MEDICATION ASSISTED TREATMENT START CARDS – OPIOID USE DISORDER

